6.5 Analysis of Safety

Safety analyses will be conducted on the SAF by dose group and overall, unless otherwise specified. No hypothesis testing will be performed.

6.5.1 Adverse Events

AEs will be coded using MedDRA and graded using the National Cancer Institute-common terminology criteria for AE (NCI-CTCAE, version 5.0).

A TEAE is defined as an AE observed after administration of the IP and up to the follow-up period. An drug-related TEAE is defined as any TEAE with a causal relationship assessed as "yes" by the investigator.

An overview summary table will include number and percentages of subjects with TEAEs, drug-related TEAEs, serious TEAEs, drug-related serious TEAEs, TEAEs leading to death, drug-related TEAEs leading to death and of all deaths. Frequencies and percentages of TEAEs and drug-related TEAEs by worst NCI CTCAE will be presented in the overview, too.

The number and percentage of subjects with TEAEs, drug-related TEAEs, serious TEAEs, drug-related serious TEAEs will be summarized by SOC and PT. The number and percentage of TEAEs by NCI CTCAE grade will also be summarized. The worst toxicity grade will be summarized if the same AE is recorded more than once for a subject.

All AE data will be listed.

6.5.2 Clinical Laboratory Evaluation

Baseline is the last measurement taken prior to IP administration.

For quantitative clinical laboratory measurements (hematology, biochemistry, urinalysis), descriptive statistics will be used to summarize results and change from baseline by dose group and time point (no overall presentation).

Quantitative laboratory test results by NCI-CTCAE Grade (version 5.0) will be summarized with frequencies and percentages by time point. Shift from baseline to the postbaseline worst grade based on NCI-CTCAE until the follow-up period in laboratory tests will be tabulated.

All laboratory data will be listed.

6.5.2.1 Liver Safety Assessment

The liver safety assessments will be summarized by the following categories below based on the measurements from Alkaline Phosphatase (ALP), Alanine Transaminase (ALT), total bilirubin, Aspartate Transaminase (AST) and their combination.

The subject's highest value post-baseline of each parameter will be used; (upper limit of normal (ULN).

- ALT: > 3xULN, > 5xULN, > 10xULN, > 20xULN
- AST: > 3xULN, > 5xULN, > 10xULN, > 20xULN
- ALT or AST: > 3xULN, > 5xULN, > 10xULN, > 20xULN
- ALP: > 1.5xULN
- Total Bilirubin: > 2xULN
- (ALT or AST > 3xULN) and Total Bilirubin > 2xULN
- (ALT or AST > 3xULN) and Total Bilirubin > 2xULN and ALP < 2xULN

The last 2 criteria where 2 or more parameters are evaluated will use the measurements on the same day or up to 1 day apart. The number and percentage of subjects meeting the criteria post-baseline will be summarized.

6.5.3 Vital Signs

Descriptive statistics will be used to summarize vital sign results and changes from baseline by dose group and time point. Baseline is the last measurement taken prior to IP administration.

Tables for potentially clinically significant vital signs will be generated using baseline value and worst value obtained post-baseline for each subject. If the criterium is checking for values greater (or equal) a specific value, the worst value is referring to the highest value obtained. If the criterium is checking for values less (or equal) a specific value, the worst value is referring to the lowest value obtained. If the criterium is a combination of two conditions, the conditions need to be fulfilled for values obtained on the same post-baseline time points to meet the criterium.

Vital Sign Variable	Criteria	
SBP	\geq 180 mmHg AND \geq 20 mmHg change from baseline	
SBP	≤ 80 mmHg	
DBP	\geq 105 mmHg AND \geq 15 mmHg change from baseline	
Pulse Rate	\geq 120 bpm AND \geq 15 bpm change from baseline	

The following potentially clinically significant criteria are defined for each parameter:

All vital signs data will be listed.

6.5.4 Electrocardiograms

ECG will be taken in triplicate. The mean values of available triplicate results will be used in the analyses.

Descriptive statistics will be used to summarize routine 12-lead ECG results and changes from baseline by dose group and time point. Baseline is the last measurement taken prior to IP administration.

Number and percentage of subjects with normal and abnormal results for the overall interpretation will be tabulated by time point. A shift analysis table showing shift in overall ECG interpretation from baseline to each time point will be provided. Percent of subjects on different kind of abnormality will also be reported.

The QT interval corrected by Fridericia's Correction formula (QTcF interval) will be summarized using frequency tables for values of clinical importance using the range criteria below.

QTcF Interval Criteria	QTcF Interval Value (msec)
Normal	\leq 450
Borderline	> 450 to <=480
Prolonged	> 480 to <=500
Clinically significant	> 500

QTcF interval: Fridericia-corrected QT interval

Cumulative tabulation for >450, >480 and >500 msec will also be presented.

The QTcF interval will also be summarized by the frequencies of subjects with a change from baseline of clinical importance using the criteria identified below.

Variable	Change from Baseline
QTcF Interval (msec)	<=0
	>0 to <=30
	>30 to <=60
	> 60

QTcF interval: Fridericia-corrected QT interval

Baseline value is latest pre-dose assessment. Cumulative tabulation for >0, >30 and >60 msec will also be presented.

All routine 12-lead ECG data and interpretations will be listed.

6.5.5 Pregnancies

A listing of all pregnancy tests will be provided.

6.6 Analysis of Pharmacokinetics

Descriptive statistics will be used to summarize plasma and spot urine concentrations of ASP5354 by dose group and time point. In addition, for each dose, descriptive statistics will be used to summarize Ae and Ae%.

All sampling dates, times, urine volumes and plasma and urine concentrations will be listed.

Pharmacokinetics will be evaluated by a population pharmacokinetics approach using concentrations of ASP5354. All details of population analyses will be described in a separate analysis plan and a separate report will be written.

6.7 Analysis of Pharmacodynamics

6.7.1 Concentration-response Relationship Analysis

The relationship between pharmacokinetics and anatomical visualization or other exploratory endpoints will be explored by a population pharmacokinetics/pharmacodynamics approach. All details of population analyses will be described in a separate analysis plan and a separate report will be written.

6.8 Other Analyses

6.8.1 Green Discoloration of Urine

The frequency and percentage of patients who experience green discoloration of urine will be summarized by dose group. The duration of green discoloration in hours will be summarized using descriptive statistics by dose group. The duration is calculated from first date/time point of green discoloration to last date/time point of green discoloration. If the green discoloration is still present at discharge, the duration is from first date/time point of green discoloration to the date/time of discharge.

Additional to descriptive statistics, if applicable, the duration will be analyzed using Kaplan Meier estimation. For this purpose, subjects with green discoloration of urine at discharge are censored at the time point of discharge.

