7.3.4 Reporting of Serious Adverse Events

Prompt notification by the investigator to the sponsor of an SAE is essential, so that legal obligations and ethical responsibilities towards the safety of subjects and the safety of a study intervention under clinical investigation are met.

In the case of an SAE, the investigator must contact the sponsor by fax or email immediately (within 24 hours of awareness).

Procedures for reporting SAEs to the sponsor are described in [Section 12.4.5 Reporting Procedures for Serious Adverse Events].

7.3.5 Disease-related Events and/or Disease-related Outcomes Not Qualifying as Adverse Events or Serious Adverse Events

Green discoloration of the urine will not be considered an AE as this is an expected, known effect of short duration without any expected untoward clinical symptoms; however, this still needs to be recorded.

Under this protocol, the following event will not be considered as an (S)AE:

- Preplanned and elective hospital/clinical procedures/interventions or procedures for diagnostic, therapeutic or surgical procedures for a preexisting condition that did not worsen during the course of the study. These procedures are collected in the eCRF.

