7.7 Other Assessments

7.7.1 Green Discoloration of Urine

The incidence of green discoloration of the urine will be recorded any time after dose administration. If it occurs, the color of urine will be assessed during surgery and every 120 minutes (\pm 30 minute window) after the end of surgery until it resolves or the subject is discharged, whichever is earlier. The start and stop date and time will also be recorded.

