5.5.3 Green Discoloration of Urine

The incidence and the duration of green discoloration of urine will be analyzed. It will be recorded any time after dose administration. If it occurs, the color of urine will be assessed during surgery and every 120 minutes (\pm 30 minutes window) after the end of surgery until it resolves or the subject is discharged, whichever is earlier. The start and stop date and time will also be recorded.

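### Green-urine duration: the descriptive table counts discharge as the end of discoloration in subjects still green, and the end point for resolved cases is not tied to the recorded stop time

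*SAP*

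**What the plan says.** Observation scheme (Protocol 7.7.1, SAP 5.5.3): once discoloration occurs, "the color of urine will be assessed during surgery and every 120 minutes" after surgery, with a ± "30 minutes window", until it resolves or the subject is discharged. No interval is given for looks during surgery. Also: "The start and stop date and time will also be recorded".

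Analysis rules (SAP 6.8.1):
- Resolved cases: "The duration is calculated from first date/time point of green discoloration to last date/time point of green discoloration".
- Unresolved cases, descriptive statistics: "If the green discoloration is still present at discharge, the duration is from first date/time point of green discoloration to the date/time of discharge".
- Kaplan-Meier: "Additional to descriptive statistics, if applicable, the duration will be analyzed using Kaplan Meier estimation". Here "subjects with green discoloration of urine at discharge are censored at the time point of discharge".

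Protocol 9.8.1 plans descriptive statistics by dose group only and has no censoring rule. Protocol 7.3.5 gives the reason discoloration is handled outside adverse event reporting: "Green discoloration of the urine will not be considered an AE as this is an expected, known effect of short duration", and it adds that no untoward clinical symptoms are expected.

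**The concern.** The SAP treats the same subjects in two ways. For Kaplan-Meier, someone still green at discharge has an incomplete duration. In the descriptive table the same value is averaged as if the urine had cleared on leaving hospital. The table is the output certain to be produced, because Kaplan-Meier depends on an applicability condition that is never defined and the protocol does not mention it.

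The second problem is the end of resolved cases. Clearing happens after the last green check and no later than the first non-green one. A rule that ends at the last green check drops that gap, and a subject seen green at only one check gets 0 h. A stop time is recorded, but neither document says whether it is the last green check, the first non-green check or a directly observed clearing.

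At stake is the description of how long a known effect lasts, which the protocol calls short. Protocol 5.1 admits subjects with eGFR from 15 to below 60 once the optimal dose is determined, and the phase 1 summary describes almost complete renal excretion. Longer discoloration in those subjects is plausible, though the documents do not show it.

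**Working it through.** The plan states no expected duration and no discharge time, so there is no plan figure to reproduce. From the documents come the check schedule and the rules above. Durations and discharge times below are assumptions.

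**1. Discharge as the end, in closed form.** With true duration T and time to discharge D, the mean loses

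loss = P(T > D) × E[T − D | T > D],

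which is never negative. Assume T log-normal, median 8 h, log-SD 0.4, measured from the end of surgery. The true mean is 8 × exp(0.4²/2) = 8.67 h.
- D fixed at 6 h: P(T > 6) = 76.4%; mean of min(T, 6) = 5.72 h; loss 2.94 h.
- D fixed at 24 h: P(T > 24) = 0.3%; mean of min(T, 24) = 8.66 h; loss 0.01 h.

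**2. Last green check as the end (literal reading).** If clearing falls evenly between checks with gap G, the mean shortfall is E[G²] / (2 E[G]). Assume times uniform within the ± 30 minute window.
- Windows timed from the previous check: G is 90 to 150 min, variance 60²/12 = 300. Shortfall (120² + 300)/240 = 61 min, maximum 150 min.
- Windows timed from the end of surgery: G is 60 to 180 min, variance 2 × 300 = 600. Shortfall (120² + 600)/240 = 62.5 min, maximum 180 min.

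**3. Both rules together, by simulation.** 4,000 subjects per scenario. Assumed: log-normal duration, log-SD 0.5; surgery ends 2.5 h after dose; looks every 15 min during surgery; log-normal discharge time, log-SD 0.4; color known at discharge. Means in hours:

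| Median duration / median discharge (h) | Still green at discharge | True mean | Cut at discharge only | Cut at discharge and last green check | Lost to discharge | Lost to last green |
|---|---|---|---|---|---|---|
| 8 / 72 | 0% | 9.10 | 9.10 | 8.07 | 0.00 | 1.03 |
| 8 / 24 | 4% | 9.15 | 8.93 | 7.95 | 0.22 | 0.98 |
| 8 / 12 | 28% | 9.16 | 7.85 | 7.12 | 1.31 | 0.73 |
| 16 / 24 | 28% | 18.30 | 15.69 | 14.95 | 2.61 | 0.74 |
| 16 / 12 | 68% | 18.15 | 11.11 | 10.78 | 7.04 | 0.33 |

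The last two columns are differences of the three before them. Across all scenarios run, resolved cases were short by 0.8 to 1.0 h on average, at most 2.9 h.

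**4. Kaplan-Meier median, same simulation (h).**

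| Scenario | Last green as event | Exact event times | True median |
|---|---|---|---|
| 8 / 24 (4% censored) | 6.64 | 8.04 | 8.04 |
| 8 / 12 (28%) | 6.74 | 8.07 | 8.06 |
| 16 / 12 (68%) | 16.27 | 16.25 | 16.10 |

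In a further run of the 16 / 12 case without a color check at discharge, 72% were censored and the last-green median was 17.95 h against 16.07 h true. Back-dated events can move ahead of censoring times, which enlarges the risk set. With two subjects, one censored at 5 h and one clearing at 6 h, the curve falls to 0 at 6 h. Back-date the event to 4 h and it falls only to 0.5 and stays there.

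**5. Candidate end points, 8 / 24 scenario.** Kaplan-Meier median: last green 6.64 h, interval midpoint 7.54 h, first non-green check 8.66 h, exact 8.04 h. Ending at the first non-green check overstates resolved durations by 0.9 to 1.1 h on average, about as much as the last-green rule understates them.

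**The case against.** The best defense is that start and stop times are recorded for this endpoint, so the first and last time points in SAP 6.8.1 may simply be those. That stands as a possible reading. If the stop time is an observed clearing, resolved cases carry no such bias; if it is the first non-green check, they are overstated by about 1 h. What remains is that the SAP does not say which.

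A reader might infer that the table and the Kaplan-Meier curve both understate duration. The documents do not support that. Kaplan-Meier already censors at discharge, so only the undefined end point can affect it, and under heavy censoring the median need not be low.

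A large discharge effect is likewise not established. The documents give no time to discharge, and with discharge at 24 h in the closed-form example the loss is 0.01 h. Dosing is intraoperative, so green time accrued in surgery makes durations of 0 h less likely and reduces the relative shortfall.

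It is also fair that short duration is only part of the protocol's reason for not counting discoloration as an adverse event, and that no threshold for short is set. A shift of an hour would not overturn that statement. None of this answers the discharge rule in the descriptive table, which is explicit.

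**Conclusion.** The concern holds on two points, at low importance. First, whenever anyone is still green at discharge, the descriptive mean is too short by a stated rule, and so is the median if many are. The loss from this rule alone was 0 to 7.0 h across the simulated scenarios in the table; where the trial falls depends on the fraction still green at discharge, which is unknown from the documents. Second, the end point for resolved cases is undefined. Read literally it costs about 1 h per case resolving between postoperative checks, at most 2.5 h or 3 h depending on how the windows are timed. Onset is also seen only when someone looks, which could shorten durations further; this was not quantified.

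The first point needs no assumption for its direction, only for its size. The second rests on reading the last green time point as a check. This is a supplementary analysis without hypothesis testing and touches neither the primary endpoint nor dose selection.

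**What to change.** Revise SAP 6.8.1, wording only:

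1. Whenever any subject is still green at discharge, make the censored estimate the main duration summary, in place of the undefined applicability condition.
2. In the descriptive table, report the number still green at discharge separately, by dose group, and do not enter discharge as a completed duration. Label any descriptive statistics that remain as covering resolved cases only, since these are a selected, shorter-lasting subset.
3. Define the end point: interval-censored between the last green and first non-green check, or the recorded stop time where clearing was directly observed. Do not set it at the first non-green check, which replaces one bias of about 1 h with its mirror image.
4. State what the recorded stop time represents.

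The cost is a little more analysis work and a somewhat longer reported duration. Provided the time of each color check is kept, no new data are needed. If only a single stop time is captured, item 4 decides how much of item 3 can be done.

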6.9 Interim Analysis (and Early Discontinuation of the Clinical Study)

The determination of dose(s) to stop, continue or define a dose as optimal will occur when every 3 subjects randomly assigned to each dose level have the data for anatomical visualization during surgery reviewed via the VRC.

6.10 Additional Conventions

As a general principle, no imputation of missing data will be done. Exceptions are the start and stop dates of AEs and concomitant medications if they are missing (see Section 6.10.2).

For the primary efficacy endpoint of anatomical visualization at 30 minutes after dosing and end of surgery, imputation will be performed in special cases when the assessment is not done at 30 minutes after dosing (see Section 5.1).

6.10.1 Analysis Windows

For efficacy analysis of anatomical visualization, assessments are summarized per time point mapped according to the following table:

	1
Time Point (post ASP5354 administration)	Collection Window
10 min	$5 \min \le \text{and} \le 15 \min$
20 min	$15 \min \le \text{and} \le 25 \min$
30 min	$25 \text{ min} \leq \text{and} < 38 \text{ min}$
45 min	$38 \text{ min} \leq \text{and} < 53 \text{ min}$
60 min	53 min \leq and $<$ 75 min
T min (every 30 minutes from 60 minutes)	T-15 min \leq and $<$ T+15 min
End of surgery	-

Table 2Mapping actual assessments times to time points

If more than one record is mapped to a specific time point, the record which is closest to the scheduled time point will be used in the analysis. In case of ties, the earlier one will be used.

For safety analyses, no mapping to analysis windows will be performed. The visit as collected in CRF will be used as analysis visit. Baseline is the last non missing assessment before ASP5354 administration.

In case of unscheduled assessments on Day 1 for vital signs, they will not be taken into account to derive Baseline, because unscheduled vital signs assessments do not provide information about the assessment time.

In safety analyses of post-baseline results (i.e. potentially clinical significant vital signs), not by time point, both scheduled and unscheduled assessments will be included to define the worst case. See also Section 6.5.2, Section 6.5.3 and Section 6.5.4.

Both scheduled and unscheduled assessments will be listed.

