6 INVESTIGATIONAL PRODUCT(S)

6.1 Investigational Product Administered

The assigned doses of ASP5354 will be administered as a single dose once the surgical area of interest is in view.

Table 4 Investigational Product(s)

Name	ASP5354
Use	Test Product
Dosage Formulation	Solution for injection
Physical Description	Clear deep green solution
Unit Dose Strength	CCI
Packaging and Labeling	ASP5354 solution will be provided in 10-mL amber glass vials and stored according to the instructions on the label
Route of Administration	Intravenous bolus infusion
Administration Instruction	Administered as a single iv bolus administration under fasting conditions, once the surgical area of interest is in view
IP or Non-IP	IP
Sourcing	Provided by sponsor

IP: investigational product

ASP5354 solution for injection should be stored between -25° and -15°C. ASP5354 vials must be allowed to thaw for at least 1.5 hours at controlled room temperature or may be thawed overnight (not more than 12 hours) under refrigerated conditions (approximately 2° to 8°C). ASP5354 vials must be used for preparation of administration within 4 hours after they are removed from the freezer or refrigerator, respectively. After thawing, the vials should be gently rotated several times to ensure a uniform concentration and to avoid foaming (the concentration in the vials is not uniform after thawing). The thawed ASP5354 is filtered and further diluted with Dextrose 5% in water. The diluted ASP5354 shall be stored at controlled room temperature (20° to 25°C) prior to administration and must be administered within (not more than) 4 hours after penetration of vials.

Refer to the pharmacy manual for detailed information regarding preparation, handling and storage of the IP.

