6.4 Investigational Product Compliance

IP will be administered intravenously at the study site by study site personnel. The exact date and time (in minutes) of IP administration will be documented.

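### SAP 6.10.1 keeps unscheduled Day 1 vital signs out of baseline because they are untimed, yet lets them into the post-baseline worst case, so a pre-dose reading can be counted as post-dose

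*SAP*

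**What the plan says.** Four rules bear on this point.

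- **Baseline.** SAP 6.10.1: "Baseline is the last non missing assessment before ASP5354 administration". For vital signs it adds: "In case of unscheduled assessments on Day 1 for vital signs, they will not be taken into account to derive Baseline". The reason given is "because unscheduled vital signs assessments do not provide information about the assessment time".
- **Worst value.** For post-baseline safety results that are not shown by time point, SAP 6.10.1 says "both scheduled and unscheduled assessments will be included to define the worst case". It names potentially clinically significant vital signs as the example. SAP 6.5.3 describes the table: "Tables for potentially clinically significant vital signs will be generated using baseline value and worst value obtained post-baseline for each subject".
- **Visit assignment.** Safety data are not mapped to windows. SAP 6.10.1: "The visit as collected in CRF will be used as analysis visit".
- **Dosing.** Protocol 6.1 has the product "administered as a single dose once the surgical area of interest is in view", so the dose falls within the operation. Protocol 6.4 adds: "The exact date and time (in minutes) of IP administration will be documented".

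Protocol Table 1 schedules Day 1 vital signs before and after the operation and leaves the intraoperative column blank. Its footnote 12 places the postoperative reading within 2 hours after surgery.

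**The concern.** The two rules in SAP 6.10.1 treat the same missing information differently. If a reading has no time, it cannot be shown to precede the dose, and that is why it is kept out of baseline. It cannot be shown to follow the dose either, yet the worst-value rule admits unscheduled readings without a Day 1 exception. Limiting the table to post-baseline values does not settle this, because the SAP says that the time needed to apply that limit is absent. Two programmers could include all such readings or none, and each could claim to follow the SAP.

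Vital signs are a secondary safety endpoint. Protocol 2.3 names hypersensitivity, including anaphylaxis, as an important potential risk, so blood pressure and pulse soon after the bolus are of interest. No vital signs are scheduled between the dose and the postoperative reading. Any value entered from that interval would be an unscheduled Day 1 reading, which is the kind that the SAP cannot place.

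**Working it through.** The plan gives no figure to reproduce. The check compares the rules and then works out the effect of one misplaced reading.

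**Step 1. Can a Day 1 unscheduled reading fall on either side of the dose?** Yes. Day 1 holds the preoperative period, the operation up to the dose, the dose, the rest of the operation and the postoperative period (Protocol Table 1 and 6.1).

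**Step 2. Does the visit label separate them?** Not by number: Protocol Table 1 gives the whole operation day as visit 2. SAP section 7 records that window mapping for safety analyses was removed in version 3.0.

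**Step 3. Does any other rule separate them?** For adverse events, yes: SAP 5.4.1 uses onset check boxes for before and after study drug on Day 1. The documents describe no counterpart for vital signs.

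**Step 4. Which rows of the SAP 6.5.3 table are exposed?**

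| Row | Level | Change from baseline also required |
|---|---|---|
| SBP high | ≥ 180 mmHg | ≥ 20 mmHg |
| SBP low | ≤ 80 mmHg | none |
| DBP high | ≥ 105 mmHg | ≥ 15 mmHg |
| Pulse high | ≥ 120 bpm | ≥ 15 bpm |

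One low systolic reading from before the dose is enough to flag a subject. The other rows also need a rise from baseline. Baseline leaves these readings out, so the rise condition narrows the exposure without removing it.

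**Step 5. Size per affected subject.** If one subject is flagged only because of a pre-dose reading, the dose-group percentage rises by 100 × 1/n. SAP 3 allows up to 15 subjects per dose level, and the Visualization Review Committee reviews in steps of 3 (SAP 2.2), so groups may be smaller.

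| n | 100 × 1/n |
|---|---|
| 15 | 6.7 points |
| 9 | 11.1 points |
| 6 | 16.7 points |
| 3 | 33.3 points |

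The n = 3 row applies only to a dose stopped at its first review. The table gives the effect per event. The expected effect also depends on how many such readings exist, which the documents do not state.

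**The case against.** The strongest reply is that the asymmetry is a cautious convention. Keeping a doubtful reading out of baseline while letting it count as a worst value errs toward over-reporting. SAP 5.4.1 does the same for adverse events: a Day 1 event with both onset boxes marked, or both blank, counts as treatment emergent. This has force. It is a good reason not to discard untimed readings, especially as an unscheduled reading may be the only value between the bolus and the postoperative measurement. However, the SAP does not state this reason for vital signs. For adverse events the convention is a fallback after a timing question has been asked; for vital signs the documents show no such question.

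Other limits also stand. The table is descriptive, and SAP 6.5 plans no hypothesis testing. All scheduled and unscheduled readings are listed. Under Protocol 12.4.1.1, a clinically significant abnormal vital sign not related to underlying disease is reported as an adverse event, so a true reaction has a second route with its own Day 1 timing. The eCRF is not among the documents, so another before/after indicator may exist on it.

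A reader might infer that the table will in fact mix readings taken under anaesthesia before the dose with post-dose ones. The documents do not support that. They do not say that anaesthetic monitor values are entered as unscheduled vital signs, and both SAP sections nominally limit the table to post-baseline values.

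**Conclusion.** The point holds as a gap in the rules: as written, SAP 6.10.1 lets an untimed pre-dose reading on the operation day count as a post-dose potentially clinically significant value. That contamination will actually occur is not shown.

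The size is 1/n per affected subject, 6.7 points in a full group of 15, with a frequency that is unknown and may be zero. This assumes that the subject has no qualifying post-dose reading and that no other eCRF item gives the order.

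The scope is narrow. Only unscheduled Day 1 vital signs are affected. The SAP's statement about missing times does not extend to ECG or laboratory data, and readings from Day 2 on are clearly post-dose. The primary endpoint is untouched. The change is worth making because it is cheap and the table is a safety display in small groups.

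**What to change.** 1. Add a clock time, or a before/after-dose flag like the one used for Day 1 adverse events, to the unscheduled vital signs record. A clock time is better: with the dose time already recorded to the minute, it also shows which pre-dose reading was last, which the baseline definition needs and a flag alone does not give.
2. For readings already entered, retrieve the time from source by query.
3. State in SAP 6.10.1 that this information decides pre- or post-dose status for both baseline and worst value.
4. For readings that remain untimed, show the potentially clinically significant vital signs table with and without them, and identify them in the listing. Excluding them outright could remove the only early values after the bolus.

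The cost is one eCRF field or a few queries, a short addition to SAP 6.10.1 and one extra display. Where a timed unscheduled reading proves to be the last before the dose, it becomes that subject's baseline under the SAP's own definition, so some change-from-baseline values may shift.
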